**Literature review**

**Introduction**

Tuberculous meningitis (TBM) is the most common type of bacterial meningitis in the Western Cape Province (WCP) of South Africa . The tuberculosis (TB) incidence in South Africa has risen from 301 new cases/100,000 population in 1990 to 948 new cases/100,000 population in 2007 , and although the world-wide incidence of the disease has fallen by an average of 1.5% per year since 2000, the incidence of the disease in South Africa is still 834 per 100, 000 population as indicated by recent World Health Organization (WHO) reports . The TB burden is worsened by the human immunodeficiency virus (HIV) pandemic. TBM represents the most severe manifestation of TB with high morbidity and mortality, despite adequate anti-TB therapy. This is mainly the result of delayed diagnosis and initiation of appropriate therapy . The pathogenesis of TB is still poorly understood. Despite ongoing research, early, cost-effective diagnostic tools are lacking . Demonstration of acid-fast bacilli and/or culture of *Mycobacterium tuberculosis* (*Mtb*) from cerebrospinal fluid (CSF) represents the gold standard for diagnosing TBM, but unfortunately the sensitivity of both these tests is low . The sensitivity of the recently developed GeneXpert

test (Cepheid Inc., USA) for TBM is ~50-60%, but only improves to 72% when CSF is centrifuged as demonstrated in a recent study . The diagnosis of TBM is therefore based on a combination of clinical, laboratory and radiological findings. However, a clinical diagnosis is often delayed, especially in the early stages of the disease when few neurological signs may be present. In addition, the CSF picture can be highly variable . Although various case definitions for TBM have been reported in the literature, diagnostic criteria vary widely, so that no standardized case definition exists . An international workshop on TBM was held during May 2009 in Cape Town, South Africa. This was attended by international experts on TBM, and a uniform case definition for TBM was proposed for future research.

### **Uniform research case definition for TBM **

It is proposed that patients suspected of having TBM be categorized into definite, probable, possible and no TBM. This is proposed to obtain standardization for research purposes, for adults and children, and was not primarily devised as a clinical tool. The clinical diagnosis of TBM (probable or possible) is based on clinical findings and special investigations (Table 1). The boundaries between groups are not fixed, and patients can interchange between groups, based on results of laboratory and radiological investigations. Definite TBM requires demonstration of acid-fast bacilli in the CSF, *Mycobacterium tuberculosis* culture from CSF, a positive nucleic acid amplification test (PCR) of CSF or histopathological evidence of *Mycobacterium tuberculosis* from a central nervous system site.

Patients must have a clinical diagnosis of meningitis including one or more of the following symptoms: headache, irritability, vomiting, fever and neck stiffness (Table 1). The diagnosis of probable or possible TBM is based on 1) clinical findings 2) CSF results 3) neuroimaging findings 4) evidence for TB outside the central nervous system and 5) additional laboratory criteria. A scoring system then determines whether a patient falls in the probable or possible TBM category (Table 1). Points are allocated for a positive finding in each of the categories, with a maximum score for each category. A total score of at least 10 is compatible with probable TBM, while a total score of at least 6 equates with a possible TBM diagnosis. A certain number of points have to come from the CSF or neuro-imaging criteria to ensure that the patient is indeed suffering from meningitis and not some other chronic type of tuberculosis. It is also suggested by the consensus

group that all patients should have additional CSF investigations to exclude alternative causes for the clinical presentation.

In practice, a clinical case definition of bacterial meningitis is needed because most patients admitted to a tertiary setting such as Tygerberg Hospital, will already have had antibiotics, which usually results in negative blood and CSF cultures . Similarly, a definite or clinical diagnosis of viral meningitis as possible cause for aseptic meningitis is critical, since aseptic meningitis is frequently caused by viruses . If an alternative cause is found for the clinical presentation, a diagnosis of not-TBM should be made, excepting where dual infection is confirmed.

### **CSF diagnosis of TBM**

It has been shown in adults that the bacterial yield of *Mycobacterium tuberculosis* can be improved by obtaining larger volumes of CSF and optimizing centrifugation . Additional measures for improving sensitivity in identification of the organism include, increasing the amount of time taken with microscopy and alternative staining methods . Based on calculations of Den Hertog *et al.*, optimal CSF centrifugation in case of mycobacterium tuberculosis infection should be at a minimum speed and duration of 3200x g for 22 minutes .

Acid-fast staining is the most rapid method for the detection of mycobacteria in clinical samples. Acid-fast staining methods include the Ziehl-Nielsen (ZN) and Auramine O stains. Since CSF is sterile, as a rule, the demonstration of acid-fast bacilli in the CSF is highly suggestive of TBM. Fluorescence microscopy uses a lower power objective lens than conventional microscopy. This enables a more rapid and cost-effective assessment of the full area of a slide. A disadvantage is the possibility of false-positive results due to inorganic objects incorporating the fluorochrome dyes . Unfortunately, the use of fluorescence microscopy has been limited in resource-poor settings by the short half-life and high cost of the traditional mercury vapour lamp. Light-emitting diode (LED) technology provides a cost-efficient alternative; it is cheap, robust and has very low energy requirements .

In response to the need for more rapid diagnosis of TB and the identification of resistant strains, nucleic acid amplification tests specific for *Mtb* have been developed. In a comparative study

between the Genotype Mycobacteria direct assay, the Gen-Probe *Mycobacterium tuberculosis* amplified direct test and the Genotype MTBDRplus for direct detection of mycobacterium tuberculosis complex in clinical samples, the Genotype MTBDRplus had the highest sensitivity (97.9%). In a study evaluating the *Mtb* complex detection rate using the Genotype MTBDRplus assay on acid-fast bacillus (AFB) smear positive sputum and PCR positive non- sputum specimens, the sensitivities were 93.8% and 77.8% respectively. For the Genotype MTBDRplus assay, the sensitivity (98.1%) and specificity (98.7%) for rifampicin resistance is very high. The accuracy for isoniazid is variable, with a lower sensitivity (84.3%) but very high specificity (99.5%). PCR is usually only done on culture. PCR on fresh CSF could potentially offer earlier confirmation of TBM diagnosis and resistance.

The GeneXpert MTB/RIF (Xpert) assay targets the rifampin resistance-associated *rpoB* gene region by heminested PCR with three specific primers and combines the sensitive detection of *M. tuberculosis* DNA and determination of rifampicin resistance using molecular beacons. Processing time is short due to automation of bacterial lysis, DNA extraction, real-time PCR amplification, and amplicon detection in a single system. High sensitivity and specificity of the Xpert assay has been shown on sputa with the assay correctly identifying 77.3% of all culture-positive specimens. Similar results are not applicable to extrapulmonary specimens, though, where the amount of mycobacterial DNA is much less. The test runs on the GeneXpert platform (Cepheid, Sunnyvale, CA) using a disposable plastic cartridge with all required reagents. Although the WHO currently recommends Xpert as an initial diagnostic test for TBM, the sensitivity of the test on CSF samples is not as high as would be obtained with sputum samples and increased to 72% when CSF was centrifuged.

### **Use of host biomarkers in the diagnosis of TBM**

Recent technological advances have made it possible to screen for many biomarkers in as little as 3 µl of sample using the Luminex multiplex cytokine beaded arrays. Using the Luminex platform, it is now possible to simultaneously detect the levels of 100 biomarkers in 3 to 50 µl (if using the Luminex/Bio-Plex 200 platform) and up to 500 markers if using the Luminex FlexMap 3D system. This platform has enabled the identification of novel host protein biomarkers for several diseases including TB. In previous studies, some of which were pioneered by our research group at

Stellenbosch University, novel biomarkers were detected in adult Quantiferon supernatants, which allowed for discrimination between TB disease and latent infection . When the biomarkers identified in adults were investigated in children, a biosignature comprising of four markers diagnosed paediatric TB disease with an accuracy of 84% .

In a recently concluded large multi-centred pan-African study (the African European Tuberculosis Consortium –[www.ae-tbc.eu](http://www.ae-tbc.eu)), we observed that some of the markers that frequently showed potential in our previous TB-antigen stimulation studies performed best either individually or in multi-marker models when measured in unstimulated supernatants. Further work on ex vivo serum biomarkers in 716 individuals that presented signs and symptoms suggestive of TB, prior to clinical diagnosis in five African countries (Namibia, Uganda, Malawi, The Gambia and South Africa), resulted in the identification of a seven-marker serum biosignature, which diagnosed TB disease in adults with high accuracy .

There are not many studies in literature that specifically employed multiplex cytokine detection platforms in the search of host biomarkers specifically for TBM. In a recently patented and published study conducted by our research group , we investigated the usefulness of some of the host markers that we identified in our previous studies as diagnostic candidates for TBM. A three-marker CSF biosignature comprising of IL-13, VEGF and cathelicidin LL-37, diagnosed TBM with a sensitivity of 52%, specificity of 95%, with positive and negative predictive values of 91% and 66% respectively . In other biomarker studies, specifically investigating the use of whole blood RNA biosignatures in the diagnosis of TB disease, it was shown that host blood-based RNA transcripts might be useful in the diagnosis of active TB disease in both adults  and children . Furthermore, a recent study identified blood RNA signature that showed potential as a biosignature for the risk of developing active TB disease . However, none of these studies have been conducted specifically in children with TBM and it is not known, whether simple blood RNA signatures such as the ones already identified for pulmonary TB might be useful in this disease. The overall aim of the current study is therefore to assess the utility of ex vivo blood and CSF based host cytokine biomarkers and RNA transcripts as diagnostic tools for TBM. We would specifically be validating the diagnostic accuracy of our previously established 3-marker TBM CSF biosignature, evaluate other new host markers which have shown potential in adult studies

but which have not been investigated in children, in more children with TBM and also RNA signatures in blood samples collected from the same children. At the conclusion of the proposed study, the validated blood-based biosignatures identified in the present study shall be ready for possible incorporation into rapid, point-of-care diagnostic tools such as the one currently being developed for adult pulmonary TB by our research group ([www.screen-tb.eu](http://www.screen-tb.eu)).

## **Hypothesis**

CSF and blood samples obtained from children with TBM will possess distinct host biosignatures in comparison to CSF and blood samples from children with other forms of meningitis and these biosignatures can be used as a tool for the rapid diagnosis of TBM.

## **Aims**

The main aims of the proposed project are as follows:

- 1) To validate a previously identified and patented three-marker CSF biosignature (IL-13, VEGF, cathelicidin LL37) for the diagnosis of TBM, in a new cohort of children with suspected TBM
- 2) To evaluate the usefulness of a recently identified and patented adult seven-marker serum protein biosignature (CRP, serum amyloid A, apolipoprotein A-1, transthyretin, complement factor H, interferon-gamma and IP-10) and other recently identified host markers, as a tool for the diagnosis of TBM
- 3) To investigate the usefulness of whole blood RNA transcripts as biosignatures for the diagnosis of TBM
- 4) To characterize the site of disease (CSF) versus peripheral blood immune profile of children with TBM, the response of immune cells to stimulation with *M.tb* antigens and explore differences between such responses in children with and those without TBM as part of student projects.
- 5) To develop a prototype point-of-care test based on host inflammatory protein biomarkers for

the rapid diagnosis of TBM (e.g. at the bedside) in children suspected of having TBM.

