### **3. Inclusion and exclusion criteria:**

All children between the ages of 3 months and 13 years with suspected meningitis, and who require CSF examination for routine diagnostic purposes at Tygerberg Children's Hospital, where written consent is obtained will be included. If possible, assent will be obtained in those children older than 7 years who have a normal level of consciousness, i.e. a Glasgow Coma Score (GCS) of 15/15. Children 13 years and older will be excluded from the study. Failure to obtain written consent will also exclude children from the study.

The anticipated study period is November 2016 to December 2025. The estimated sample size, using a two-sample comparison of proportions (STATA®-Statistics/Data Analysis), required for each of the diagnostic aims of the study includes, at least, 72 children with definite or probable TBM and a total sample size of up to 460 patients (This includes children with TBM, bacterial

meningitis, viral meningitis and normal CSF). An average of 40 new TBM cases is admitted to our wards annually.

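### Aims 1 and 5 concern children with suspected TBM, but enrolment takes any suspected meningitis and the analysis pools all non-TBM children, so specificity may be overstated for the population the aims name

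*Combined protocol and SAP*

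**What the plan says.** - **Aims.** Aim 1 places the validation of the CSF signature "in a new cohort of children with suspected TBM". Aim 5 is a prototype for "the rapid diagnosis of TBM (e.g. at the bedside) in children suspected of having TBM". Aim 2 (the serum signature and other markers) does not name suspected TBM.
- **Section 3, Inclusion and exclusion criteria.** Entry is open to "All children between the ages of 3 months and 13 years with suspected meningitis, and who require CSF examination for routine diagnostic purposes", subject to consent. Suspicion of TBM is not required. The target is at least "72 children with definite or probable TBM and a total sample size of up to 460 patients", and the total is said to include TBM, bacterial "meningitis, viral meningitis and normal CSF". No number is given for any control group.
- **Statistical methods and analysis plan.** Biomarker concentrations are compared between participants with TBM and those without. The sentences on ROC curves and multi-marker models name no other comparator. Tests for more than two groups are mentioned, but only for comparing levels. No specificity by control group or among TBM suspects is planned.
- **Use of host biomarkers in the diagnosis of TBM.** The pilot figures for the signature are sensitivity 52% and specificity 95%.

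**The concern.** Specificity belongs to the mix of non-diseased children in whom it is measured, not to the test alone. The aims ask how the signature performs when a clinician is wondering about TBM. The non-TBM children in that group are likely to be the hard ones, for example those with subacute, lymphocytic or partially treated disease. The plan adds every other child who needs a lumbar puncture for suspected meningitis, including children whose CSF proves normal. If the signature is more often negative in those added children, the pooled figure will look better than a user would see among suspects. Removing the normal-CSF children would not settle the matter, because acute bacterial or viral meningitis in children not suspected of TBM would remain.

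What is at stake is the validation claim. A pooled specificity near the pilot's 95% would read as replication and support carrying the markers into the aim 5 test, even if performance among suspects were clearly worse. As written, the plan would not show the difference.

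**Working it through.** **1. Whether the populations differ.** Aims 1 and 5 name suspected TBM. Inclusion asks for suspected meningitis. The analysis contrast is TBM against all others. The set analysed is thus wider than the set in the aims, and no step in the analysis plan narrows it.

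**2. The plan's own figures.** The sample size is described as "using a two-sample comparison of proportions", without the proportions, power, sidedness or allocation ratio, so the 72 can be neither confirmed nor refuted. Several settings give it: 55% against 80%, 1:1, two-sided 5%, 90% power gives 72 per group, and so does 70% against 90%, 1:1, two-sided 5%, 80% power with continuity correction. The figures serve here only to bound the controls. With at least 72 TBM cases and at most 460 children, there are at most 460 − 72 = 388 children without definite or probable TBM.

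**3. Formula.** Let w be the share of controls who were TBM suspects.

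- Pooled specificity = (1 − w) × Sp(non-suspects) + w × Sp(suspects)
- Overstatement for suspects = (1 − w) × [Sp(non-suspects) − Sp(suspects)]

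The documents give neither w nor the two specificities. All values below are assumptions.

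**4. Illustration with 99% in non-suspects and 85% in suspects.**

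| w | Calculation | Pooled specificity |
|---|---|---|
| 20% | 0.8 × 0.99 + 0.2 × 0.85 | 96.2% |
| 30% | 0.7 × 0.99 + 0.3 × 0.85 | 94.8% |
| 50% | 0.5 × 0.99 + 0.5 × 0.85 | 92.0% |

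At w = 30% the pooled figure matches the pilot's 95% almost exactly, while the false-positive rate among suspects is 15%, not 5%. With 0.30 × 388 ≈ 116 non-TBM suspects, that means 116 × 0.15 ≈ 17 false positives, against 116 × 0.05 ≈ 6. If all 72 TBM cases were suspects and sensitivity were 52%, there would be 72 × 0.52 ≈ 37 true positives. The positive predictive value among suspects would then be 37.4 / (37.4 + 17.4) ≈ 68%, against 37.4 / (37.4 + 5.8) ≈ 87%.

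**5. Sensitivity to the assumptions.** Pooled minus suspect specificity, in percentage points:

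| Non-suspects / suspects | w = 75% | w = 50% | w = 25% |
|---|---|---|---|
| 98% / 85% | +3.25 | +6.5 | +9.75 |
| 98% / 90% | +2.0 | +4.0 | +6.0 |
| equal | 0 | 0 | 0 |
| 85% / 95% | −2.5 | −5.0 | −7.5 |

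The sign follows the difference between the two groups. The last row is what would happen if the added controls were the harder ones.

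**6. Precision among suspects.** With 116 non-TBM suspects and specificity 85%, the half-width of the 95% interval is 1.96 × √(0.85 × 0.15 / 116) = 0.065, or about ±6.5 points. The 116 rests on the upper bound of 388, so a real subset could be smaller and the interval wider.

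**The case against.** **Broad enrolment is defensible.** Prospective inclusion of every child needing a CSF examination is sound, and the Hypothesis section contrasts TBM with other forms of meningitis, which fits it. Aim 5 states an intended use, not an enrolment rule. This stands as an argument for keeping the enrolment. It does not answer aim 1, which names the validation cohort as suspected TBM.

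**A reader might infer that specificity will be inflated.** The documents do not support that. They give no control mix and no group-specific specificities, and the shift can be positive, zero or negative. Bacterial meningitis is also an inflamed CSF state and need not be an easy negative. Upward bias is the plausible direction, above all from normal-CSF children, but it is not established.

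**A reader might also infer that TBM was never in question in the added children.** The documents do not say so. The Introduction calls TBM the commonest bacterial meningitis in the province. Section 2 describes a tertiary hospital that receives suspected-TBM referrals. Section 4 lists TB staining, culture and nucleic acid tests without limiting them to suspects. The literature review says most children admitted to such a setting have already had antibiotics, so hard controls may be common. Routine TB testing does not, however, show that the clinician suspected TBM in a given child.

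**Making suspects the only primary population would carry its own bias.** The Introduction notes that diagnosis is often delayed early in the disease, when neurological signs are few. TBM cases not suspected at lumbar puncture would drop out, which would change sensitivity and could take the TBM count below 72. This stands, and it is why the full cohort must be reported alongside.

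**The data sheet was not available.** The clinical evaluation form and data capture sheet are addenda outside the supplied text and may already record suspicion, referral reason or symptom duration. Even so, the analysis plan makes no use of such a field.

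**388 is a ceiling.** At about 40 TBM admissions a year over November 2016 to December 2025 (110 months, 9.17 years), full enrolment of TBM would give about 367 cases, leaving about 93 places for controls within 460.

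**Conclusion.** The mismatch between the aims, the inclusion criteria and the analysis contrast is plain in the text. As written, the analysis estimates specificity in a population wider than the one aim 1 names, and the figure may be overstated for children with suspected TBM. The documents do not allow the size to be computed. The 96.2%, 94.8% and 92.0% rest wholly on assumed specificities of 99% and 85% and assumed suspect shares of 20%, 30% and 50%. Other assumptions move the shift between a gain of almost 10 points and a loss of 7.5.

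The point is that the plan cannot show whether a bias exists. It does not establish certain inflation, and it does not justify replacing the full cohort with suspects alone. It should be settled before biomarker results are linked to diagnoses, because suspicion is easy to record before CSF results and can only be approximated afterwards.

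**What to change.** 1. **Enrolment.** Leave the inclusion criteria as they are, and state that the population of aims 1 and 5 is the suspected-TBM subset of the enrolled cohort.
2. **Data sheet.** Add one yes/no item, completed before CSF results: whether TBM is in the differential diagnosis. For children already enrolled, derive it from clinical data that preceded the results (such as symptom duration, TB contact and reason for referral), where recorded, by a rule fixed before biomarker data are linked.
3. **Analysis plan.** Pre-specify sensitivity and specificity, with 95% intervals, in suspected-TBM children as the estimate that answers aim 1 and the evaluation of the aim 5 test. Always report it beside the full suspected-meningitis cohort.
4. **Reporting.** Give specificity separately for bacterial, viral and normal-CSF controls, and give the number of TBM cases not suspected at lumbar puncture.

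The cost is one data item and a few sentences. The suspect estimate will rest on fewer controls and possibly fewer TBM cases, with an interval of about ±6.5 points in the 116-suspect example and wider if controls are fewer. The headline specificity will probably be less favourable. The derived item for past enrolments will be less reliable than one recorded prospectively.
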